Every patient included will be registered for baseline values, and will then be followed for ECMO management and transfusion management daily for the first two weeks and weekly during the following two weeks or until ECMO weaning if the ECMO run will be shorter than the observation time. During the first two weeks of observation, daily parameters will be recorded. Moreover, data will be recorded for every PRBC, Plasma, Platelets transfusion event. The patients will be observed for the clinical outcomes until they are discharged from the ICU and 6-months mortality will be recorded. Considering that according to the Extracorporeal Life Support Organization summary, the average length of respiratory ECMO run is about 12 days we believe that the majority of ECMO run will be fully covered by the observation period and, at least, it will be paradigmatic of a center's actual practice and, at the same time, will assure a considerable sample size of transfusion events.

Data will be reported according to the STROBE (Strengthening the reporting of observational studies in epidemiology) statement checklist.

The knowledge about this topic may not be achieved differently by other study design like retrospective studies or surveys. In fact, in 2017, ESICM endorsed a survey on the topic (data presented at the ECISM congress 2018) that showed a strong variability among centers about blood products transfusions, but the level of evidence achieved by a survey is low. Moreover, to explore retrospectively datasets of published studies would not allow to highlight the current practice and the strength of the study rely on the length that is one year and will surely cover the current technological frame considering a rapidly evolving scenario.

Study population: inclusion criteria/patient selection

All patients who receive extracorporeal lung support (ECMO) for ARDS respiratory causes will be included. Of note, considering the observational design of our study, patients can be included in other studies concurrently (this will be noted on the CRF).

Exclusion criteria: refusal to include

Jehovah's witnesses and all patients refusing transfusions for personal reasons will not be excluded if a valid informed consent is acquired, but they will be analyzed separately.

Study conduction

The study will be conducted in compliance with the current Helsinki Declaration and the standards of good clinical practice.

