The protocol will be entered into a public database (www.clinicaltrials.gov).

Given the explorative nature of this study, the required number of patients was not calculated, but considering at least 10 patients/year for each center (considered the worst prediction) we imagine that the included patients will be at least 100 in Italy and we presume to enroll at least a double number worldwide.

Study duration

- Transfusions decisions for each patient will be recorded daily during a two-week period after ECMO cannulation and weekly for the subsequent two weeks, or until the end of ECMO support if the length is < 28 days.
- Patients will be observed until ICU discharge with a follow up to sixth months for mortality
- The inclusion period will be 12 months for each center.

Data collection methods

Data will be recorded using pre-printed CRF by the principal investigator (PI) in each center or directly they will be recorded online. All data will be reported in a centralized online and Web-based fully encrypted database (REDCAP). The study coordinator will regularly contact the local PI to ensure data collection and reporting as well as completion of patient follow-up.

Moreover the study coordinator, available at ISMETT, will keep regularly updated the local investigators on the data recorded and will help in keeping in touch with local PI or if authorized will keep in touch with eventual hospitals or other sanitary residency where the patients are transferred. In the management of the study the data manager available at ISMETT will be dedicated to the goal of reducing to the minimal the loss of data also with the follow up.

The access to the REDCAP database will be regulated by personal credentials (username and password) so that each investigator will have granted specific levels of access (read-only, data entry, or full-administrative privileges).

Every participating center will have to ask the permission to their Ethic Committee or other relevant and competent authorities according to the local rules.

Data will include clinical characteristics: baseline demographics, basic biological values (e.g., blood gas, hemoglobin), primary diagnosis, comorbidities, underlying etiology of acute respiratory failure, severity of illness (e.g., SOFA, SAPS 2), type of ECMO, and the size of the cannulas.

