ECMO management data will be collected daily for the first 28 days. Additionally, fluid balance, adverse events, Hb and all hematological data, anticoagulation management and monitoring will be collected every 24 hours.

Data will also be collected for the duration of mechanical ventilation, duration of ECMO, and ICU length of stay. Clinical outcome assessment will be made, with date of death, ICU discharge, hospital discharge, sixth month mortality.

Statistical Analysis

Descriptive statistics including frequency (percentage), median and interquartile range (IQR) will describe overall population and groups of survivors and non-survivors.

In order to describe current transfusion practice the amount of PRBC, Plasma and Platelets, will be described as units and ml and as a number of transfusions adjusted for ECMO length of stay and considering the concomitant bleeding episodes.

Fibrinogen and Antithrombin III will be described as mg or units respectively and as a number of administration.

Anticoagulation will be reported as type, mean dosage and the confidence interval (CI 95%).

Hb average level and the confidence interval (CI 95%) will be reported.

Baseline categorical and continuous variables will be compared for transfusion and ECMO weaning groups. In particular categorical variables will be compared with chi-square tests and continuous variables will be compared with Student's T-test, or Wilcoxon rank-sum tests, otherwise.

Multiple COX regression analysis will be used in order to explore the impact of confounding factors such as baseline patient severity, ECMO length of stay, bleeding episodes and possible others covariates and factors that will be observed and raised relevance during the first exploratory or univariate analysis. The impact of relevant confounding factors such as length of ECMO run, pre-ECMO severity scores, pre-ECMO administration of transfusions will be analyzed separately and together in multiple analyses.

In particular daily RBC transfusion will be studied according to the association to renal function, fluid balance, worst Hb level, episodes of bleeding, use of vasopressors, ECMO blood flow.

A p-value less of than 0.05 will be considered significant. Data handling and analyses will be done with SAS 9.4 software (SAS Institute Inc, Cary, NC, USA) and R 3.3 software (R Foundation for Statistical Computing).

Patient data Collection

For each included patient the investigators will collect the following data:

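### Hb and anticoagulant-dose CIs have no stated averaging unit, and no allowance for patient or centre correlation is named for them, for daily RBC transfusion or, for centre, in the Cox models

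*Combined protocol and SAP*

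**What the plan says.** The Statistical Analysis section commits to two interval estimates: "Hb average level and the confidence interval (CI 95%) will be reported", and "Anticoagulation will be reported as type, mean dosage and the confidence interval (CI 95" percent). Neither sentence gives the unit of averaging.

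Under Data collection methods, "Hb and all hematological data, anticoagulation management and monitoring will be collected every 24 hours", so each patient contributes repeated values. Study Design adds that the anticoagulation parameter and its target follow each centre's own protocol.

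Two model-based analyses are planned, with significance at p < 0.05:
- "Multiple COX regression analysis will be used in order to explore the impact of confounding factors". The covariates named include severity, ECMO duration and bleeding, and the list is left open to others that emerge from exploratory work. Centre is not named.
- "In particular daily RBC transfusion will be studied according to the association to renal function, fluid balance, worst Hb level", among other daily covariates. No model is given.

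No mixed model, GEE, frailty or cluster-robust variance is named anywhere. The nearest text is under Predefined subgroup analyses: an Hb trigger profile for each centre, and exploratory strata by centre workload and geography. These are descriptive and correct no standard error.

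The recording schedule after day 14 is stated in different ways:
- Study Design has ECMO and transfusion management followed "daily for the first two weeks and weekly during the following two weeks".
- Study duration has transfusion decisions "recorded daily during a two-week period after ECMO cannulation and weekly for the subsequent two weeks".
- Data collection methods says "ECMO management data will be collected daily for the first 28 days".

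**The concern.** A mean over patients and a mean over patient-days are different quantities whenever Hb or dose is related to run length. Two competent analysts could follow this plan and report different averages with different intervals.

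The data have two levels of correlation: days within a patient, and patients within a centre that follows local practice. An ordinary CI for a mean ignores both. In the daily RBC analysis, ordinary methods would treat correlated days as independent. In the regression models the error can go either way: standard errors tend to be too small for covariates that vary mainly between clusters, and can be too large for those that vary mainly within them. What is at stake is the precision reported for Hb and dose, and the p-values from the exploratory models.

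**Working it through.** The plan has no figure to reproduce. Study conduction says that the sample size was not calculated, and no ICC is given. The cross-centre variability reported in Study Design concerns blood products, not Hb or dose, so every ICC below is an assumption.

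**Inputs from the documents**
- Cap of 20 patients per centre (Study Design).
- 10 patients per centre per year, offered as a pessimistic forecast (Study conduction).
- Average run of about 12 days (Study Design).
- At least 100 patients in Italy and at least double that worldwide (Study conduction). At 10 per centre this suggests 100/10 = 10 Italian centres and 200/10 = 20 in all. The count of 20 is inferred, not stated.

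**One value per patient, centre correlation only, equal centre sizes**

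Design effect DE = 1 + (m − 1) × ICC, with m patients per centre. Coverage of a naive 95% CI = 2Φ(1.96/√DE) − 1.

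| m | ICC | DE | Coverage |
|---|---|---|---|
| 5 | 0.01 / 0.05 / 0.15 | 1.04 / 1.20 / 1.60 | 94.5 / 92.6 / 87.9% |
| 10 | 0.01 / 0.05 / 0.15 | 1.09 / 1.45 / 2.35 | 94.0 / 89.6 / 79.9% |
| 20 | 0.01 / 0.05 / 0.15 | 1.19 / 1.95 / 3.85 | 92.8 / 84.0 / 68.2% |

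Example: m = 20 and ICC 0.05 give DE = 1 + 19 × 0.05 = 1.95, and 1.96/√1.95 = 1.40, so coverage is 84.0%.

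**Patient-days pooled as independent, within-patient correlation only**

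With 12 daily values and within-patient ICC 0.3 / 0.4 / 0.5, DE = 1 + 11 × ICC = 4.3 / 5.4 / 6.5, and coverage is 65.5 / 60.1 / 55.8%.

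**Simulation check (20 equal centres, 20,000 runs, ICC 0.01 / 0.05 / 0.15)**

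| Interval and target | 10 per centre | 20 per centre |
|---|---|---|
| Naive, centres a sample from a wider population | 93.9 / 89.3 / 80.3% | 92.9 / 83.8 / 68.4% |
| Naive, participating centres as fixed target | 95.0 / 95.3 / 96.8% | 95.4 / 95.8 / 96.8% |
| Centre-clustered, t on 19 df, wider target | 94.9 / 94.7 / 95.1% | 95.1 / 94.9 / 95.0% |
| Width ratio, clustered t to naive | 1.10 / 1.27 / 1.62 | 1.15 / 1.47 / 2.07 |

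Without a small-sample correction, the clustered interval covered 92.5% to 93.1%. With unequal centres of 3 to 20 patients, a separate 8,000-run check of the clustered t interval gave 94.2% to 94.6%. A more uneven layout gave 93.2% to 94.3%.

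**Weight of a long run in a patient-day mean**

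Under daily recording to day 28, a 28-day run counts 28/7 = 4.0 times a 7-day run. Under daily then weekly recording, assuming two weekly records, it counts (14 + 2)/7 = 2.3 times. In a mean over patients it counts once.

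**The case against.** The strongest reply is that this is an exploratory, descriptive study whose primary blood-product summaries carry no CI, so only two secondary summaries and some exploratory p-values are touched. That limits the consequence. It does not justify an interval whose unit is unstated, and the plan still sets a significance threshold.

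Several stronger readings are tempting and are not supported:
- **That the Hb and dose CIs will cover only 56% to 66%.** This requires pooling patient-days as independent, which no section says will be done. One average per patient is equally open and removes that source.
- **That centre clustering must make the CIs too narrow.** This depends on the target. Aim of the study describes real practice in a large number of centres, and the worldwide ambition for the results appears under Expected Results. For the participating centres alone, a naive CI is about nominal. No sampling of centres is described, so clustered variance does not by itself establish worldwide inference.
- **That 10 per centre is a floor.** It is a forecast. Predefined subgroup analyses foresees centres with fewer than 10 runs a year. The publication section asks for at least 10 per investigator, with two investigators per centre, which can be read as 20. At 5 per centre the effect is milder.
- **That centre is barred from the Cox models.** The open covariate list would allow it. It is simply not pre-specified.
- **That the whole weekly/daily conflict applies to Hb and dose.** The Study duration text covers transfusion decisions only. The 24-hourly Hb sentence gives no duration, although the Summary gives 28 days for blood tests. Only runs beyond day 14 are affected.

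**Conclusion.** The omission is certain and worth correcting. The averaging unit for Hb and dose is undefined. No allowance for patient or centre correlation is named for those CIs or for daily RBC transfusion, and centre is not pre-specified in the Cox models.

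The size is uncertain, because it rests on assumed ICCs, equal centre sizes and a target wider than the participating centres. On those terms, with one value per patient, a nominal 95% CI is close to nominal at ICC 0.01 and falls to between 88% (5 per centre) and 68% (20 per centre) at ICC 0.15. The lower figures for pooled days show what the ambiguity permits, not what the plan states. No size is claimed for the daily RBC or Cox analyses. This is a point the sponsor should address, but no confirmatory conclusion depends on it.

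**What to change.** 1. Define the Hb and dose means as the mean over patients of each patient's own average on ECMO, with dose summarised within each anticoagulant drug.
2. Compute the CI with centre-clustered robust variance and a t multiplier on (centres − 1) degrees of freedom. A linear mixed model is not interchangeable here, because it weights patients and centres differently and so changes the mean being estimated.
3. Analyse daily RBC transfusion (yes/no) with a logistic mixed model with random intercepts for centre and for patient within centre, and report the odds ratios as conditional.
4. In the Cox models, use centre-clustered robust errors or a shared centre frailty, named in advance.
5. Separately, reconcile the recording schedules after day 14 in Study Design, Study duration and Data collection methods, and state how unequal recording is handled.

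The cost is SAP wording and modest programming in SAS or R, both already named; no new data are needed. Intervals for means widen by about 1.10 to 1.62 times at 10 per centre and 1.15 to 2.07 times at 20, assuming 20 equal centres and the ICCs above.

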Study Design: international multicenter prospective observational cohort study.

For the primary outcome PRBC will be evaluated as total amount during the ECMO run and for the first 28 days as daily amount. The total amount of PRBC, adjusted for the ECMO length of stay, will be evaluated in light of pre-ECMO parameters (age, comorbidities, postoperative state and severity scores) and of daily data (bleeding episodes, ECMO blood flow, dieresis, CRRT, Hb, major events). Daily occurrence of PRBC transfusion will be described according to pre-ECMO characteristics and daily parameters (Hb, bleeding, hemodynamics, renal function, circuit change).

Plasma, platelets, Fibrinogen, Antithrombin III administration will be evaluated according to pre-ECMO data and according to daily APTT level (or other coagulation monitoring adopted), bleeding episodes, sepsis.

For the secondary outcomes type of anticoagulant will be described as well as daily dose and daily target for the parameter targeted (APTT, ACT, r-TEG, anti-Xa according to local protocol). Anticoagulation will be described in relation to pre-ECMO parameters and daily episodes of bleeding and occurrence of sepsis.

Bleeding episodes will be described according to site (airway – including tracheotomy - oro-nasal, gastric, intrathoracic, abdominal, intestinal, retroperitoneal, urinary tract, other) and classified according to severity following 5 adjusted categories of the Bleeding Academic Research Consortium (BARC) score: Type 0, no bleeding; Type 1, Any overt bleeding that requires heparin infusion rate reduction or PRBC transfusion (provided Hb drop was related to bleeding); Type 2, any overt bleeding that requires heparin infusion rate reduction and packed red blood cells transfusion or non-surgical procedure to stop bleeding (provided Hb drop was related to bleeding); Type 3, Any life-threatening bleeding that required PRBC transfusion and surgical intervention for control of bleeding or ECMO discontinuation; Type 4: any fatal bleeding.

The study is prospective and, consequently, in each center all consecutive adult patients who are eligible according to inclusion and exclusion criteria should be included in the study up to 20 patients.

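### Unadjusted baseline tests between undefined transfusion groups take no account of time on ECMO, so they mix predictors of run length with predictors of transfusion rate

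*Combined protocol and SAP*

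**What the plan says.** The Statistical Analysis section states that "Baseline categorical and continuous variables will be compared for transfusion and ECMO weaning groups". It specifies that "categorical variables will be compared with chi-square tests", that continuous variables get a Student's t-test or Wilcoxon rank-sum test, and that "A p-value less of than 0.05 will be considered significant". None of these tests contains ECMO days. The section does not say what a transfusion group is: which product, whether yes/no or a cut in amount, or over what period. This point concerns the transfusion groups only, not the weaning groups.

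Time at risk differs between patients. Under Study Design, "For the primary outcome PRBC will be evaluated as total amount during the ECMO run and for the first 28 days as daily amount". Under Study duration, transfusion recording covers up to four weeks "or until the end of ECMO support if the length is < 28 days".

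Elsewhere the plan does deal with run length. Under Study Design, "The total amount of PRBC, adjusted for the ECMO length of stay, will be evaluated in light of pre-ECMO parameters", and daily PRBC occurrence is to be described by pre-ECMO characteristics. The Statistical Analysis section describes the number of transfusions adjusted for ECMO length and lists run length among the confounders for the multivariable work. It gives no method for the adjustment and attaches none to the group tests. It also lets factors that stand out in exploratory or univariate analysis join the Cox regression.

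**The concern.** Each further day on ECMO is another opportunity to be transfused. If patients are grouped by what they received over the run, those who die early or recover quickly tend to fall in the untransfused or low-amount group because they were observed for less time. A baseline factor that only lengthens or shortens the run can then appear as a correlate of transfusion. A factor that raises the daily rate but shortens the run can be missed. In a study meant to describe transfusion practice, a significant p-value here would readily be read as showing who tends to be transfused. It could also decide which additional covariates enter the multivariable models.

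**Working it through.** **Inputs from the protocol.** Mean run: "the average length of respiratory ECMO run is about 12 days" (Study Design; no SD given). Level 0.05, taken as two-sided because sidedness is not stated. Sample size: "the required number of patients was not calculated" (Study conduction), but at least 100 patients are expected in Italy and at least double worldwide, so 200 is used. The plan states no power or effect size, so there is no figure of its own to reproduce.

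**Assumed, because the protocol gives no figure.** Transfusion rate *h* of 0.05 to 0.30 per day; shape of the run-length distribution; in the simulation, between-patient variation in rate (frailty variance 0.5) and a binary baseline factor with 50% prevalence and ratio 1.5.

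**Step 1. Run length by group when everyone has the same daily rate.** For exponential runs with end-of-run hazard *m* = 1/12:

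- P(never transfused) = *m*/(*h*+*m*)
- mean run if never transfused = 1/(*h*+*m*)
- mean run if ever transfused = [12 − P(never) × mean(never)] / [1 − P(never)]

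At *h* = 0.1: P(never) = 0.0833/0.1833 = 45.5%; mean(never) = 1/0.1833 = 5.5 days; mean(ever) = (12 − 0.455 × 5.45)/0.545 = 17.5 days.

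| *h* per day | Never transfused | Mean run, never (days) | Mean run, ever (days) |
|---|---|---|---|
| 0.05 | 62.5% | 7.5 | 19.5 |
| 0.10 | 45.5% | 5.5 | 17.5 |
| 0.20 | 29.4% | 3.5 | 15.5 |
| 0.30 | 21.7% | 2.6 | 14.6 |

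Less variable runs (gamma, shape 4, mean 12) have mean(never) = 12/(1+3*h*) and P(never) = (1+3*h*)^−4. At *h* = 0.1 this gives 12/1.3 = 9.2 against 13.5 days; at 0.3, 12/1.9 = 6.3 against 12.5 days. Capping observation at 28 days, the exponential figures become 5.6 against 15.3 days (*h* = 0.1) and 2.6 against 13.1 (*h* = 0.3). The size depends on the assumptions; the direction does not change.

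**Step 2. Why the tests cannot separate the two effects.** With exponential runs of mean μ, P(ever) = *h*μ/(1+*h*μ), which depends only on the product of rate and mean run length. Starting from *h* = 0.1 and μ = 12, *h*μ = 1.2 and P(ever) = 1.2/2.2 = 54.5%.

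- Run 1.5 times longer, same rate: 0.1 × 18 = 1.8, so 1.8/2.8 = 64.3%.
- Rate 1.5 times higher, same run: 0.15 × 12 = 1.8, again 64.3%.
- Rate 1.5 times higher, run 1.5 times shorter: 0.15 × 8 = 1.2, back to 54.5%.

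The mean total count is also *h*μ, so grouping by total amount has the same weakness.

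**Step 3. Effect on the tests.** Simulation with 200 patients, gamma runs of shape 1 or 2, *h* from 0.05 to 0.30, no 28-day cap, and 1,000 replicates (800 for the rate model). The comparator is a Poisson model with a log(ECMO days) offset and robust standard errors. Entries are the percentage of trials with p < 0.05, as ranges over the settings.

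| Factor truly acts on | Ever/never groups | Above/below median total | Rate model |
|---|---|---|---|
| neither | 4–6% | 4–6% | 4–8% |
| run length only (×1.5) | 22–31% | 22–46% | 4–7% |
| daily rate only (×1.5) | 21–31% | 25–44% | 42–81% |
| rate ×1.5, run length ÷1.5 | 5–7% | 5–6% | 43–79% |

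Part of the rate model's higher power in the third row comes from using counts instead of two groups. The second and fourth rows show the effect of accounting for time.

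**The case against.** The plan already contains the better analysis. Under the primary outcome it relates length-adjusted total PRBC, and daily PRBC occurrence, to pre-ECMO characteristics, and it names run length as a confounder. The group tests are one unadjusted comparison in a study that calls itself explorative. The groups are undefined and might be built on a length-adjusted amount. Who is transfused at any point in a run is also a fair descriptive question, for which run length is partly the mechanism and not a nuisance.

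Much of this stands, and it limits the point. A reader might infer four stronger things that the documents do not support:

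- *That the plan forms the groups over the whole run.* This is the natural reading, since no early window or landmark is given, but it is not stated.
- *That the tests detect run length and not transfusion.* They respond about equally to both (22–31% against 21–31% for ever/never groups). A factor with no effect on either is flagged at close to the nominal rate.
- *That the plan ignores run length.* It does not.
- *That the univariate tests decide the covariates.* Severity, ECMO length of stay, bleeding and pre-ECMO transfusion are named in advance; univariate results only add to them.

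What remains is that none of the planned adjustments is attached to these tests, and their method is not specified. The Cox step is not a clear repair: its outcome is not stated, and ECMO length of stay is known only when the run ends. The descriptive question can be answered without p-values.

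**Conclusion.** The point holds in limited form. The group tests have no time-at-risk term. If the groups reflect transfusion over the run, the tests mix effects on run length with effects on transfusion rate, and can miss a factor that moves the two in opposite directions. The damage is confined to these comparisons and to covariates added because of them; the length-adjusted descriptions of the primary outcome are not affected.

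Among 200 patients, a factor that changes only run length by a ratio of 1.5 would be called significant in 22–31% of trials with ever/never groups, against 4–7% with a rate model. These sizes rest on assumed transfusion rates, run-length shapes and factor effects, with only the 12-day mean taken from the plan. The missing definition of the groups is a gap whatever those values are.

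**What to change.** In the Statistical Analysis section:

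1. Replace the tests between transfusion groups by a model of PRBC transfusions per ECMO day: a count model with a log(ECMO days) offset and robust or overdispersed errors, or a day-level model. Count and days must cover the same window, because PRBC is totalled over the run while recording is described up to day 28. This also supplies the method missing from the length adjustment planned under Study Design.
2. If a time-to-event form is preferred, use the cause-specific hazard of first PRBC, censored at end of ECMO or death. The cumulative incidence with end of ECMO as a competing event does not solve the problem: over the run it equals the ever-transfused proportion in step 2, which still depends on run length.
3. Choose any added covariates from these results, not from the unadjusted tests.
4. Define the transfusion groups (product, cut, window). Show any ever/never table descriptively, without p-values and with ECMO days beside it.

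Cost: changed wording and slightly more analysis work, and the simple group p-values are lost. Transfusion events and ECMO duration are already collected. The offset model assumes that expected transfusions rise in proportion to days; a day-level model relaxes this. Before using daily covariates after day 14, the plan should reconcile weekly follow-up in weeks three and four (Study Design, Study duration) with daily collection to day 28 (Data collection methods).
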